9.4.1. Primary Analyses

The primary endpoints will be analyzed using logistic regression. The statistical model on which the inference will be based will include terms for treatment, centre, type of baseline controller (ICS alone vs. ICS/LABA), gender and age. Centre, as the unit of randomization, will be treated as a random effect. The results of the primary analyses will be presented as point estimates, 95% confidence intervals and associated p-values for the adjusted mean differences between ACT guided treatment and usual care.

Analyses of the primary endpoints will be performed on the ITT population and the PP population; the ITT population is considered primary.

9.4.2. Secondary Analyses

All secondary endpoints will be confined to the ITT population.

Continuous efficacy endpoints will be analyzed using analysis of covariance (ANCOVA) and adjusted for centre as a random effect. For daytime and night-time symptom score, the same method (ANCOVA adjusted by centre) will be used if the parametric model assumptions hold. The assumptions of normality and homogeneity of variance will be assessed by inspection of normal probability plots and residual plots. If these assumptions are not met, alternative methods (e.g., nonparametric methods) may be performed in order to assess the robustness of the conclusions from the primary analysis.

For time to event endpoint, stratified log-rank test and Cox regression analysis will be performed with centre, type of baseline controller (ICS alone vs. ICS/LABA), gender and age as the stratification factors. Kaplan-Meier methodology will be used to estimate median time for each treatment arm. Kaplan-Meier curves will be constructed to provide a visual description of the difference between the two treatment arms.

9.4.3. Other Analyses

Asthma exacerbation rate will be analyzed using logistic regression as described for the primary endpoints.

Interactions between treatment and each of the covariates will be investigated in turn, with all main effects in the model regardless of their statistical significance. Any

interaction terms found to be statistically significant will be explored and if necessary results will be reported for each level of the covariate. Investigation of interactions will be confined to the primary endpoints. The effect of interactions (e.g., treatment by centre) will be assessed at the 10% level of significance.

Adverse events

The number (%) of subjects in each treatment group with treatment emergent AEs will be produced. Counts and percentages will also be presented of subjects with serious adverse events (SAEs), AEs leading to withdrawal, AEs by severity and AEs by relationship to study drug.

Other safety measures

Reason for withdrawal will be summarised.

Summary statistics for vital signs evaluations at each visit will be presented by treatment group. In addition, summary statistics for change from baseline for vital signs evaluations will be presented by treatment group.

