5.3. Withdrawal/Stopping Criteria

The primary reason for the subject discontinuing from the study will be recorded in the Case Record Form. The investigator must determine the primary reason for discontinuation. The end of study/early discontinuation procedures must be performed at the time of discontinuation from the clinical study.

The subject **must** be discontinued from the study for any of the following reasons:

1. A subject is significantly non-compliant with treatment or the requirements of the protocol;
2. Lost to follow up;
3. Subject's decision not to participate any further (withdrawal of consent);
4. In the investigator's opinion, it is in the subject's best interest;
5. Subjects experience a protocol-defined asthma exacerbation;
6. The study is terminated by the Sponsor or designee;
7. Pregnancy (Subject should notify investigator immediately on becoming pregnant).

A subject may withdraw from study treatment at any time at his/her own request, or may be withdrawn at any time at the discretion of the investigator for safety, behavioural or administrative reasons.

The reason(s) for subjects not completing the study will be recorded in the Case Report Form (CRF), and that the investigator must document, if applicable, the reason (if specified by the subject) for withdrawal of consent. The end of study/early discontinuation procedures must be performed at the time of discontinuation from the clinical study.

The following actions must be taken in relation to a subject who fails to attend the clinic for a required study visit:

- The site must attempt to contact the subject and re-schedule the missed visit as soon as possible.
- The site must counsel the subject on the importance of maintaining the assigned visit schedule and ascertain whether or not the subject wishes to and/or should continue in the study based on previous non-compliance.
- In cases where the subject is deemed 'lost to follow up', the investigator or designee must make every effort to regain contact with the subject (where possible, 3 telephone calls and if necessary a certified letter to the subject's last

known mailing address or local equivalent methods). These contact attempts should be documented in the subject's medical record.

- Should the subject continue to be unreachable, only then will he/she be considered to have withdrawn from the study with a primary reason of "Lost to Follow-up".

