7.1. Time and Events Table

ACTIVITY	Visit 0	Visit 1	Visit 2	Visit 3	Visit 4	Visit 5	Visit 6 (or Early Withdrawal)
Study Week (Visit Window)	0	4w±1	8w±1	12w±1	16w±1	20w±1	24w±1
Informed consent	x						
Randomization/Allocation of clusters	x						
Subject Demography	x						
Medical history	x						
Verification of inclusion/exclusion criteria	x						
Efficacy Evaluation							
Verification of withdrawal criteria		x	x	x	x	x	x
Issue diary record cards	x	x	x	x	x	x	
Collect/Review diary record cards		x	x	x	x	x	x
Compliance assessment		x	x	x	x	x	x
Asthma control Test (ACT) score	x	x	x	x	x	x	x
AQLQ(S)	x						x
Lung function Test	x						x
Safety Evaluation							
Adverse event assessment ¹	x	x	x	x	x	x	x

1. Serious AEs will be recorded from the time the consent form is signed until the follow-up visit. All AEs will be recorded from the start of study treatment until the follow-up visit.

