7.3.3. Other Endpoint (s)

- Rate of moderate/severe asthma exacerbation over the 24-week treatment period

Asthma Exacerbations

Subjects who experience worsening of symptoms should:

- increase relief medication usage for relief of symptoms
- contact the investigator or primary physician immediately and report to the clinic as soon as possible (ideally within 24 hours)
- record their symptoms, PEF and relief medication usage in their DRC, as previously instructed

- if intervention therapy is required during a treatment period, subjects may receive oral corticosteroids (40-60 mg prednisolone daily, or equivalent, for 10 days), over and above their usual asthma medication.

Exacerbations will be assessed by the physician at each scheduled visit by reviewing the DRC, as well as specific questioning on adverse events (AEs).

Exacerbations will be defined based on one or more of the following characteristics:

Definition of asthma exacerbation(s)

Moderate

A moderate asthma exacerbation is defined as a deterioration in asthma requiring treatment with an oral corticosteroid.

Individual courses of oral corticosteroids are classified as separate exacerbations only if they are administered >1 week apart. Any course started within one week of finishing the previous course is considered part of the previous exacerbation.

Severe

A severe asthma exacerbation is defined as a deterioration in asthma which requires hospital admission.

Time/date of resolution

Time/date at which the exacerbation has resolved, in the opinion of the investigator and/or subject.

Details of exacerbations must be collected in the Asthma Exacerbations page of the CRF and DRC as follows at the Visit immediately following the exacerbation:

Date of onset and resolution, daily morning PEF during the exacerbation; details of management of the exacerbation (e.g. clinic or emergency room visit, self-managed, hospital admission etc.); restriction/prevention from continuing usual activities. An exacerbation resulting in hospitalization will be recorded as a serious adverse event (SAE) in the Serious Adverse Event pages of the CRF. However, it is not only these exacerbations resulting in hospitalization which require collection as SAEs, but those that meet any of the definitions of Seriousness, listed in Section 7.4.

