7.3. Exploratory Efficacy Analyses

Moderate/severe asthma exacerbations will be summarized, including number of subjects with moderate/severe exacerbations, number of moderate/severe exacerbations and characteristics of moderate/severe exacerbations. Exacerbations separated by less than 7 days will be treated as a continuation of the same exacerbation

The moderate/severe exacerbation rate will be analyzed using a generalized linear model, assuming the number of exacerbations has a negative binomial probability distribution and that its mean is related to covariate factors with a 'log link' function. The logarithm of time (year) on study will be used as an offset variable. All moderate/severe

exacerbations observed during the study, with the onset date of event from date of baseline visit to the end of study visit date or early withdrawal (from study) visit date, will be included in the analysis. Missing data due to early withdrawal from the study will not be imputed. The model will include covariates for treatment, baseline ACT total score, type of baseline controller (ICS alone vs. ICS/LABA), gender and age. The annual moderate/severe exacerbation rates and 95% confidence interval for each treatment will be presented. The rate ratio and 95% confidence interval, percent reduction in rate and 95% confidence interval and P value will also be presented.

The example SAS codes are as below:

```
proc genmod data= input_data;  
  class rndgrp blcontrol gender;  
  model no_exac = rndgrp actbl blcontrol gender age / dist=negbin  
link=log offset=logtime wald type3;  
  lsmeans rndgrp / cl diff OM exp;  
run;
```

where input_data is the name of the input dataset and no_exac is the number of moderate/severe asthma exacerbations per subject during the study. In terms of the covariates rndgrp, actbl, blcontrol, gender and age are variables for randomised treatment code, baseline ACT total score, type of baseline controller, gender and age respectively. For offset, logtime is logarithm of time (year) on study.

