8.1. Adverse Events Analyses

The number (%) of subjects in each treatment group with treatment emergent AEs will be produced. Counts and percentages will also be presented of subjects with serious adverse events (SAEs), AEs leading to withdrawal, AEs by severity, AEs by relationship to study procedure/study drug, asthma exacerbation and death.

Adverse events will be coded by MedDRA version 21.0 or above. Adverse events will be summarized and presented by system organ class (SOC) and preferred term (PT) by treatment group. Adverse events analyses including the analysis of AEs, SAEs, non-serious AE and other significant AEs will be summarized. All AEs and SAEs will be listed. The details of the planned displays are provided in [Appendix 8: List of Data Displays](#).

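### Adverse events are summarised only as crude percentages of subjects, although an exacerbation ends AE follow-up; if exits differ by arm, one row mixes two opposing distortions

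*Protocol*

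**What the plan says.** **AE measure.** Protocol 9.4.3: "The number (%) of subjects in each treatment group with treatment emergent AEs will be produced". It continues: "Counts and percentages will also be presented of subjects with serious adverse events (SAEs), AEs leading to withdrawal, AEs by severity". SAP 8.1 repeats this and extends the list to "AEs by relationship to study procedure/study drug, asthma exacerbation and death". Neither section mentions person-time, exposure-adjusted incidence or time to first event for AEs.

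**Exit rule.** Protocol 5.3 lists the reasons for which a subject must leave the study. Item 5 is: "Subjects experience a protocol-defined asthma exacerbation".

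**AE window.** The footnote to the protocol 7.1 schedule says: "All AEs will be recorded from the start of study treatment until the follow-up visit". The last scheduled column is Visit 6 or early withdrawal. Under protocol 7.4.1.1, investigators need not look for AEs in subjects who have left.

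**Where time is allowed for.** For the moderate/severe exacerbation rate only, SAP 7.3 plans a negative binomial model: "The logarithm of time (year) on study will be used as an offset variable".

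**Whether an exacerbation is an AE.** Protocol 12.2.1 counts worsening of a pre-existing condition as an AE, but excludes the disease under study unless it is more severe than expected. Protocol 7.3.3 makes a hospitalised exacerbation an SAE.

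**Text that points the other way on exit.** Protocol 7.3.3 says: "if intervention therapy is required during a treatment period, subjects may receive oral corticosteroids". It collects details at the next visit and says when successive steroid courses count as separate exacerbations. SAP 7.3 models a count per subject.

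**The concern.** A crude percentage compares arms fairly only if subjects in both arms are watched for about the same time. Here, AE observation can end because of an outcome on which the arms are compared. The arm with more exacerbation exits has less time in which other AEs can be recorded, so its percentage of those AEs falls even when the underlying risk is equal.

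The exacerbation that causes the exit may itself be recorded as an AE or SAE. That raises the any-AE percentage in the same arm, and it puts exits made by rule into the row for AEs leading to withdrawal, next to exits for events that were not tolerated. A reader of a single crude row cannot separate the two effects. At stake is whether the AE tables can say anything clear about harm from score-driven treatment adjustment compared with usual care.

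**Working it through.** **Plan figures used.** Protocol 9.2.1: 35 evaluable subjects per centre and 20% dropout. 35 / (1 − 0.20) = 43.75, rounded to 44; 44 × 12 = 528, as stated. This is 264 per arm. The dropout is not split by arm or reason. The plan gives no AE rate, exacerbation rate or exposure figure, so what follows is an illustration on assumed inputs.

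**Assumptions.** The AE hazard is constant and equal in both arms. AE risk over a full 24 weeks is p = 30%. A fraction e of each arm exits, evenly over the 24 weeks, and other exits are ignored.

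**Step 1: AEs other than the exacerbation.**
- Hazard over 24 weeks: L = −ln(1 − p) = 0.3567.
- AE risk of a subject who exits: q = 1 − (1 − exp(−L)) / L = 1 − 0.30 / 0.3567 = 0.159.
- Crude percentage: (1 − e) × p + e × q.

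**Step 2: the exacerbation exit is itself counted as an AE.** Every exiting subject then has an AE, so the any-AE percentage is (1 − e) × p + e.

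| Exits e | Mean time on study, 1 − e/2 | Other AEs, crude | Any AE if exacerbations count |
|---|---|---|---|
| 5% | 97.5% | 0.285 + 0.008 = 29.3% | 33.5% |
| 15% | 92.5% | 0.255 + 0.024 = 27.9% | 40.5% |
| 10% | 95.0% | 0.270 + 0.016 = 28.6% | 37.0% |
| 30% | 85.0% | 0.210 + 0.048 = 25.8% | 51.0% |

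The gap for other AEs is (difference in e) × (p − q). At 5% v 15% it is 0.10 × 0.141 = 1.4 points (ratio 0.95). At 10% v 30% it is 0.20 × 0.141 = 2.8 points (ratio 0.90). If exits are equal it is zero. Counting exacerbations as AEs reverses the order: 33.5% v 40.5%, and 37% v 51%.

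**Step 3: range over the AE risk.** At p = 10%, p − q = 0.049; at p = 50%, p − q = 0.221. The gap therefore runs from 0.5 to 2.2 points at 5% v 15%, and from 1.0 to 4.4 points at 10% v 30%.

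**Step 4: a second model.** With exits also at a constant hazard (AE and exit as competing hazards), p = 30% gives 29.3% v 27.8% at exits of 5% v 15%, and 28.6% v 25.5% at 10% v 30%. For AE risks of 10% to 50% and exits from 5% v 10% up to 10% v 30%, the gap is 0.3 to 4.8 points. The arm with more exits is lower in every case.

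**Step 5: does a rate remove the gap?** Time to first event or exit, as a fraction of 24 weeks, has mean (1 − e) × p / L + e × q / L, because a uniform exiter contributes q / L on average. This is the crude percentage divided by L. First events divided by this time therefore give L in both arms, a rate ratio of 1.00 whatever e is.

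**The case against.** **The arm with more exits looks safer.** A reader might infer this from Step 1. The documents do not support it as a general statement. It holds only for AEs other than the exacerbation. Protocol 12.2.1 may let exacerbations into the AE tables, and protocol 7.3.3 makes hospitalised ones SAEs; the order then reverses. If the disease-under-study exclusion keeps non-serious exacerbations out, the complaint about the withdrawal row largely falls away for those events.

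**The effect is small.** This stands. Exits of 10% v 30% at 264 per arm are 26 + 79, about 106 subjects. That is the whole planned 20% dropout, three times as heavy in one arm. If half of the dropout were exacerbation exits (53 subjects), 5% v 15% would already be a marked imbalance, and it gives 1.4 points. The standard error of a 30% v 30% difference at 264 per arm is √(2 × 0.3 × 0.7 / 264) = 4.0 points before clustering. Putting all exits at Week 4 would give 27.6% v 22.7%, but nothing in the documents suggests that timing.

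**Subjects may stay on study.** Protocol 7.3.3 and SAP 7.3 read that way, and the mechanism weakens if they do. Against this, item 5 is worded as mandatory, and other exits shorten follow-up too.

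**The mixing is partly visible already.** Protocol 9.4.3 summarises reasons for withdrawal. SAP 8.1 gives asthma exacerbation its own line and tabulates by SOC and PT, and SAP 8.2 singles out asthma. This helps, but it does not take exacerbations out of the any-AE row or split the AE-withdrawal row. The table shells are in a separate document, so what they add is unknown.

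**Safety reporting is descriptive.** True: no between-arm safety test is planned. This limits the consequence but does not make the crude percentages easier to interpret.

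**Conclusion.** The point holds in a limited form. Both documents plan AEs only as crude subject percentages, while one listed exit rule ties the length of AE follow-up to an outcome compared between arms. If exits differ by arm, other AEs are under-counted in the arm with more exits. If exacerbations count as AEs, the any-AE and AE-withdrawal rows are pushed the opposite way.

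Under the even-exit assumptions above, the spurious gap in other AEs is about 1.4 points at exits of 5% v 15% and 2.8 points at 10% v 30%, and nil with equal exits. The documents fix neither the size nor the existence of an imbalance: they give no AE rates and forecast no difference in exits. The sample size and the primary analysis are untouched. The exacerbation rate already has its own time offset. This is a cheap improvement to the safety tables, not a flaw that threatens the trial's conclusions.

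**What to change.** In protocol 9.4.3 and SAP 8.1, keep the crude counts and percentages and add:

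1. A summary of time on study by arm.
2. First-event incidence per 100 subject-years (subjects with a first event, over time from Visit 0 to first event or exit) for any AE and any SAE, each with and without asthma exacerbation events, and by SOC/PT where feasible.
3. A split of AEs leading to withdrawal into exits under protocol 5.3 item 5 and all others.

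Read the between-arm safety summary from these alongside the crude counts. Separately, reconcile protocol 5.3 item 5 with protocol 7.3.3 and SAP 7.3 on whether a subject remains on study after an exacerbation. State also how the disease-under-study exclusion in protocol 12.2.1 applies to non-serious exacerbations.

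**Cost.** No new data, visits or subjects are needed, only some SAP wording and extra table columns. Time on study is already needed for SAP 7.3, but it runs to study end or withdrawal, so time to first event must be newly derived. That derivation is limited by AE dates that are missing or partial, which SAP 10.5.2.1 leaves unimputed. The rates assume a roughly constant hazard and exits unrelated to AE risk. The second may fail for exacerbation exits, which is why the crude counts should stay beside the rates.

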10. STUDY GOVERNANCE CONSIDERATIONS

10.1. Posting of Information on Publicly Available Clinical Trial Registers

Study information from this protocol will be posted on publicly available clinical trial registers before enrollment of subjects begins.

10.2. Regulatory and Ethical Considerations, Including the Informed Consent Process

The study will be conducted in accordance with all applicable regulatory requirements, and with GSK policy.

The study will also be conducted in accordance with International Council for Harmonisation (ICH) Good Clinical Practice (GCP), all applicable subject privacy requirements, and the guiding principles of the current version of the Declaration of Helsinki. This includes, but is not limited to, the following:

- IRB/IEC review and favorable opinion/approval of the study protocol and amendments as applicable
- Signed informed consent to be obtained for each subject before participation in the study (and for amendments as applicable)
- Investigator reporting requirements (e.g. reporting of AEs/SAEs/protocol deviations to IRB/IEC)
- GSK will provide full details of the above procedures, either verbally, in writing, or both.
- Signed informed consent must be obtained for each subject prior to participation in the study
- The IEC/IRB, and where applicable the regulatory authority, approve the clinical protocol and all optional assessments, including genetic research.
- Optional assessments (including those in a separate protocol and/or under separate informed consent) and the clinical protocol should be concurrently submitted for approval unless regulation requires separate submission.
- Approval of the optional assessments may occur after approval is granted for the clinical protocol where required by regulatory authorities. In this situation, written approval of the clinical protocol should state that approval of optional assessments is being deferred and the study, with the exception of the optional assessments, can be initiated.

10.3. Quality Control (Study Monitoring)

- In accordance with applicable regulations including GCP, and GSK procedures, GSK monitors will contact the site prior to the start of the study to review with the site staff the protocol, study requirements, and their responsibilities to satisfy regulatory, ethical, and GSK requirements.
- When reviewing data collection procedures, the discussion will also include identification, agreement and documentation of data items for which the CRF will serve as the source document.

GSK will monitor the study and site activity to verify that the:

- Data are authentic, accurate, and complete.
- Safety and rights of subjects are being protected.
- Study is conducted in accordance with the currently approved protocol and any other study agreements, GCP, and all applicable regulatory requirements.

The investigator and the head of the medical institution (where applicable) agrees to allow the monitor direct access to all relevant documents

10.4. Quality Assurance

- To ensure compliance with GCP and all applicable regulatory requirements, GSK may conduct a quality assurance assessment and/or audit of the site records, and the regulatory agencies may conduct a regulatory inspection at any time during or after completion of the study.
- In the event of an assessment, audit or inspection, the investigator (and institution) must agree to grant the advisor(s), auditor(s) and inspector(s) direct access to all relevant documents and to allocate their time and the time of their staff to discuss the conduct of the study, any findings/relevant issues and to implement any corrective and/or preventative actions to address any findings/issues identified.

